5.4. Treatment Compliance

Compliance with study drug administration will be verified through observation by study staff or trained home healthcare professionals.

5.5. Other Requirements

5.5.1. Contraception

Females of child-bearing potential must be willing to use a highly effective method of contraception from 14 days before first dose, throughout study participation, and for 12 weeks after the last dose of study drug in this study.

Birth control methods which are considered highly effective include:

- Placement of an intrauterine device.
- Placement of an intrauterine hormone-releasing system.
- Bilateral tubal occlusion.
- Surgical sterilization of male partner (with the appropriate post-vasectomy documentation of the absence of sperm in the ejaculate; for female patients on the study, the vasectomized male partner should be the sole partner for that patient).
- Established use of oral (except low-dose gestagens), implantable, injectable, or transdermal hormonal methods of contraception.
- True sexual abstinence, when in line with the preferred and usual lifestyle of the patient. Periodic abstinence (eg, calendar, ovulation, symptothermal, post-ovulation methods) and withdrawal are not acceptable methods of contraception. Abstinent patients must agree to use one of the above-mentioned contraceptive methods if they

start heterosexual relationships during the study and for up to 12 weeks after the last dose of study drug.

Investigators should advise females of childbearing potential of the most appropriate birth control method available within their country taking into account local medical practice.

Females of child-bearing potential include female patients who have experienced menarche (or begin menarche over the course of the study), and who are not postmenopausal or permanently sterilized (eg, bilateral tubal occlusion, hysterectomy, or bilateral salpingectomy). A postmenopausal state is defined as the absence of menses for 12 months without an alternative medical cause, confirmed by follicle stimulating hormone level within the postmenopausal range.

For male patients, no contraception is required. However, use by males of contraception (condom) may be required in some countries, eg, France, in order to comply with local requirements as described in the corresponding patient informed consent forms.

Compliance with contraception requirements will be assessed on a regular basis by the Investigator throughout the course of the study (see Section [6.5.5.2](#)).

6. STUDY ASSESSMENTS

The Schedule of Assessments is provided in [Table 1](#) (double-blind period) and [Table 2](#) (open-label extension period). Additional information on the collection of study assessments will be detailed in the respective reference manuals.

6.1. Screening Assessments

An ICF that has been approved by the appropriate Institutional Review Board (IRB)/Independent Ethics Committee (IEC) must be signed by the patient or legal guardian before the Screening procedures are initiated. All patients or their legal guardians will be given a copy of the signed and dated ICF. In addition, a medical records release form will be required of all patients for the purpose of obtaining vital status information from the patient's physician or from death registries.

See the Schedule of Assessments ([Table 1](#)) for a list of Screening visit assessments.

Patients will be screened to ensure that they meet all the inclusion criteria and none of the exclusion criteria. Rescreening (once) of patients is permitted with consultation of the Medical Monitor (see Section [6.1.2](#)).

Patient demographic data and medical history/disease history will be obtained, including completion of ophthalmologic history in the eCRF. Any changes to medical history occurring between the screening assessment and Day 1 will be updated prior to study drug administration.

If a genetic test result that shows the presence or absence of a TTR pathogenic mutation, which would be consistent with either wtATTR or hATTR, is not available at Screening for the assessment of eligibility (Section [4.1](#), inclusion criterion 2a), genotyping may be conducted at a laboratory selected by the site in consultation with the Medical Monitor.

The study eligibility biopsies and technetium scintigraphy noted in inclusion Criterion 2 are intended to be historical, as part of the patient's clinical care and diagnosis, and are not performed as part of the study.

An echocardiogram will be performed at screening Visit 1 and results confirmed centrally to assess study eligibility, as indicated in the Schedule of Assessments ([Table 1](#)).

6.1.1. Retesting

If in the Investigator's judgement, the screening laboratory abnormalities are likely to be transient, then laboratory tests, may be repeated. The Investigator's rationale should be documented. Laboratory values can be retested once during screening provided that the patient can be evaluated for eligibility and randomized within the allowed Screening period. Any additional repeat testing may be considered after discussion with the Medical Monitor.

6.1.2. Rescreening

A patient who does not meet all study eligibility criteria due to a transient condition observed at screening, or who fails to complete screening activities due to unforeseen or unavoidable circumstances, may be rescreened once after consultation with the Medical Monitor after a minimum of 5 days have elapsed from a patient's last screening assessment. A patient will be re-consented if rescreening occurs outside of the 45-day screening window. In this case, all screening procedures must be repeated.

6.2. Efficacy Assessments

6.2.1. 6-Minute Walk Test (6-MWT)

The 6-MWT, which will be assessed as the primary endpoint, is an assessment of functional exercise capacity. The 6-MWT will be administered by staff trained in the procedure per the relevant study manual. The staff administering the 6-MWT will be different from the Investigator or designee managing the care of the patient.

The 6-MWT will be performed at each of the timepoints specified in the Schedule of Assessments ([Table 1](#) and [Table 2](#)). At screening Visit 1, the 6-MWT will be administered for study eligibility purposes (per inclusion Criterion 6 [Section 4.1]). At screening Visit 1, prior to conducting the 6-MWT, the site staff will familiarize the patient with the purpose and conduct of the 6-MWT, as described in detail in the relevant study manual. Familiarization can be repeated at other timepoints if deemed helpful.

On Day 1 (baseline), which is a dosing day, the 6-MWT will be performed prior to study drug administration. (No other dosing days have a 6-MWT assessment.)

Patients who are hospitalized during the study should wait at least 2 weeks after hospitalization before completing a 6-MWT assessment; less time post-hospitalization may be permitted if, in the opinion of the investigator, the patient is unencumbered due to the recent hospitalization. In addition, if a patient is not feeling well due to an external factor (eg, flu, sprained ankle, pulled back muscle) at a visit when the 6-MWT will be performed, the test should not be done and should be rescheduled for another day within the permitted visit window.

For each 6-MWT assessment, the site should make every effort to have this assessment performed by the same assessor and to perform the test at approximately the same time of day. If the test is interrupted or deemed unusable by the 6-MWT core laboratory, the 6-MWT should be repeated as soon as possible within the allowed visit window.

Further details regarding the 6-MWT are provided in the relevant study manual.

A 1.5-month window will be used to group 6-MWT assessments to the Month 6 (Weeks 25-26), Month 9 (Weeks 37-38), and Month 12 (Weeks 52-53) visits. During the double-blind period, a patient may opt to begin tafamidis treatment or to discontinue study treatment, in which case they would complete a Pre-tafamidis Drop-in Visit ([Table 1](#)) or Early Treatment Discontinuation Visit ([Table 2](#)), respectively. To avoid the potential training effect from repeated assessments of the 6-MWT within a short period of time, only one 6-MWT assessment should be collected for the following time periods: Day 2 to Day 214 (for Month 6), Day 215 to Day 319 (for Month 9), and Day 320 to Day 372 (for Month 12).

Within a given time period, the 6-MWT assessment should be performed at whichever visit occurs first (scheduled assessment, Pre-tafamidis Drop-in Visit, or Early Treatment Discontinuation Visit); no additional 6-MWT assessments should be made in that time period. In later time periods, the 6-MWT should be assessed per the Schedule of Assessments ([Table 1](#)).

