3.5. Method of Assigning Patients to Treatment Groups

Using the interactive response system (IRS), patients will be randomized 1:1 to the patisiran or placebo arm. Randomization will be stratified by:

1. Baseline tafamidis (yes vs no)
2. Genotype (hATTR vs wtATTR amyloidosis with cardiomyopathy)
3. NYHA Class I or II **and** age < 75 years vs all other

Each patient will be uniquely identified in the study by a combination of the site number and patient identification number. Upon signing the informed consent form (ICF), the patient will be assigned a patient identification number by the IRS. The Investigator or his/her designee will contact the IRS to randomize the patient after confirming that the patient fulfills all the inclusion criteria and none of the exclusion criteria.

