7.1. Determination of Sample Size

The planned enrollment for this study is 300 patients. For the change from baseline at Month 12 in the 6-MWT, assuming a treatment difference of 33 meters between patisiran and placebo in the treatment-naïve group and 20 meters in patients with baseline tafamidis, the weighted average treatment difference between patisiran and placebo in the overall population is approximately 29 meters (standard deviation = 75 meters) assuming 70% are in the treatment-naïve group and 30% are in the baseline tafamidis group. A sample size of 300 patients provides >90% power for a 2-sided test to detect a mean difference between treatment groups at a 2-sided alpha = 0.05. Additional patients may be enrolled based on a recommendation to increase the sample size in the interim assessment ([Section 7.2.10](#)).

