7.2.5.1. Primary Endpoint

The primary endpoint, change from baseline at Month 12 in the 6-MWT, will be analyzed using a mixed-effects model repeated measures (MMRM) approach. The outcome variable is change

from baseline in the 6-MWT. The model will include the baseline value as a covariate, treatment, visit, the treatment-by-visit interaction, baseline tafamidis (yes vs no), genotype (hATTR vs wtATTR), and age (<75 vs \geq 75 years) as fixed factors, and patient as a random effect. The primary comparison is the contrast (difference in least squares [LS] means) between the patisiran and placebo groups at Month 12.

Sensitivity analyses will be detailed in the SAP.

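### The primary model leaves out the screening 6-MWT, a second pre-randomization walk that every eligible patient already has; adding it would modestly sharpen a valid analysis

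*Protocol*

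**What the plan says.** Inclusion Criterion 6 (section 4.1) requires at least 150 m on the 6-MWT at screening, so every eligible patient has a screening distance. Section 6.2.1 states the purpose of that test: "At screening Visit 1, the 6-MWT will be administered for study eligibility purposes". The same section labels a separate pre-dose walk on Day 1 as baseline.

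Section 7.2.5.1 fixes the terms of the primary MMRM for change in 6-MWT: "The model will include the baseline value as a covariate, treatment, visit, the treatment-by-visit interaction". It then adds baseline tafamidis, genotype and age group, with patient as a random effect. The synopsis gives the same list. The screening walk is not in it, and no part of the text shown gives that walk a role in the analysis.

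On size, section 7.1 says: "A sample size of 300 patients provides >90% power for a 2-sided test".

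This is the Amendment 1 text. The summary of changes for Amendment 2 lists no change to the primary model or to the use of the screening walk.

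**The concern.** The outcome is change from Day 1, so the Day 1 test error is part of it. Adjusting for the Day 1 value removes only some of that error, because one walk cannot tell a patient's true capacity from how the test went that day. A second pre-treatment walk, taken during a screening period of up to 45 days, carries further information on this point.

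The screening walk comes before randomization, so adding it cannot bias the comparison. An average learning effect between the two walks is the same in both arms and goes into the intercept. At stake is the width of the primary confidence interval. The protocol itself notes in section 7.2.10 that tafamidis drop-in could cost power, and it allows for enrolling more patients in response.

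**Working it through.** **Inputs from the protocol.** Section 7.1: "The planned enrollment for this study is 300 patients". Section 3.5: "patients will be randomized 1:1 to the patisiran or placebo arm", hence 150 per arm. Section 7.1 also gives the effect, "assuming a treatment difference of 33 meters between patisiran and placebo in the treatment-naïve group and 20 meters in patients with baseline tafamidis", and the weights, "assuming 70% are in the treatment-naïve group and 30% are in the baseline tafamidis group". The SD is 75 m and alpha is 0.05, two-sided.

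**Step 1: the plan's own figure.**
- Weighted effect: 0.7 × 33 + 0.3 × 20 = 29.1 m, stated as about 29 m.
- Standard error: 75 × √(2/150) = 8.66 m. Ratio: 29/8.66 = 3.35.
- Power: 91.8% by the normal approximation and 91.6% by the noncentral t. The claim of more than 90% is reproduced.

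**Step 2: model for the gain.** Write the screening walk as T + e_s, the Day 1 walk as T + e_0 and the Month 12 walk as T + D + e_12. T is true capacity with SD s_T, and each test error is independent with SD s_e. D is true change, independent of T. Taking 75 m as the SD of observed change gives Var(D) = 75² − 2s_e². Then:

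- Residual variance = Var(T | walks) + Var(D) + s_e²
- With k pre-treatment walks, Var(T | walks) = s_T²(s_e²/k) / (s_T² + s_e²/k)

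The values of s_T and s_e are **assumptions**, since the documents give neither. The ranges used are s_T 80 to 120 m and s_e 15 to 35 m.

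**Step 3: worked case, s_T = 100 m, s_e = 30 m.**
- Var(D) = 5625 − 1800 = 3825.
- Day 1 only: 10000 × 900/10900 = 825.7. Total: 825.7 + 3825 + 900 = 5550.7 (SD 74.5 m).
- Day 1 plus screening: 10000 × 450/10450 = 430.6. Total: 5155.6 (SD 71.8 m).
- Reduction: 1 − 5155.6/5550.7 = 7.1%. The interval narrows by 1 − √(5155.6/5550.7) = 3.6%.

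**Step 4: the range.** Power is by noncentral t with 150 per arm and 29 m. Equivalent N is 300 divided by (1 − reduction).

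| s_T, s_e (m) | Variance reduction | Interval narrower by | Power, Day 1 only → both | Equivalent N |
|---|---|---|---|---|
| 80, 15 | 1.9% | 1.0% | 91.6% → 92.1% | 306 |
| 100, 20 | 3.4% | 1.7% | 91.7% → 92.5% | 310 |
| 100, 30 | 7.1% | 3.6% | 91.9% → 93.7% | 323 |
| 100, 35 | 9.4% | 4.8% | 92.2% → 94.4% | 331 |
| 120, 35 | 9.8% | 5.0% | 92.0% → 94.3% | 333 |

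**Step 5: less favourable conditions.**
- *Learning that varies between patients.* Suppose it adds a variance of 25² = 625 to the screening walk. Then Var(T | walks) = 1/(1/10000 + 1/900 + 1/1525) = 535.7, and the total is 5260.7. The 7.1% gain becomes 5.2%. With stronger patient-to-patient learning it falls further.
- *Shared noise.* If the test error were wholly common to the two walks, the second would repeat the first and the gain would be zero.

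The honest range is therefore from near 0% to about 10%, with 5% to 7% as the central expectation.

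**The case against.** The strongest reply is that nothing here is an error. Adjusting for the Day 1 value with tafamidis, genotype and age is a standard, valid model, and the stated power is correct. That stands in full.

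The second reply is that parsimony was a deliberate choice. Amendment 1 took NYHA class out of this model because it correlates with baseline 6-MWT, and a second walk would correlate with it more strongly. The rationale is real and the fix should acknowledge it, but it does not carry over. NYHA class was judged largely redundant with the baseline walk. A repeat of the endpoint measure adds information on the Day 1 test error, which NYHA class does not supply.

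The third reply concerns size. The working model is favourable:
- It assumes equal and independent error at both walks and no true change between them.
- The screening walk is the first one, given just after familiarization, and section 6.2.1 itself raises a training effect from repeated walks within a short period.
- Entry is truncated on the screening value, which a normal model ignores.

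These points stand. They are why the range has to reach down to nearly zero.

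A reader might infer that 91.6% shows a thin or underpowered trial. The documents do not support this: the claim is more than 90%, and it is met. The 91.6% is also an unadjusted t-test figure, while the planned model already adjusts for Day 1.

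**Conclusion.** The point holds as a missed efficiency, not as a flaw. A pre-randomization measurement that every eligible patient has is left out of a model that could use it without bias. The expected benefit is a fall in residual variance of about 5% to 7%, within a range from near 0% to about 10%. That means roughly 0 to 2.5 points of power and an interval up to about 5% narrower.

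These figures rest on assumed values for the between-patient SD and the test error, on approximate independence of the errors at the two walks, and on complete data. A larger gain can be calculated: a screening to Day 1 correlation of 0.85 with a baseline SD of 120 m gives 15.9%. But that implies a test error SD of 120 × √0.15 = 46 m, beyond the range used here, and nothing in the documents supports relying on it.

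Nor should a reader conclude that the primary analysis is biased or invalid without the change. It is neither. Two limits on the reading remain: the SAP is not shown and could define the baseline value more broadly, and the model text cited is that of Amendment 1.

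**What to change.** Before unblinding, add the screening 6-MWT as a second continuous covariate beside the Day 1 value in section 7.2.5.1 and the synopsis. Apply the edit to the current version of the protocol and carry it into the SAP. Enter it as a separate term rather than averaging it with Day 1, because learning may make the two walks unequal. Keep change from Day 1 as the outcome, and use the same covariates in the 6-MWT sensitivity analyses. One sentence should say why this term is added although NYHA class was dropped for parsimony.

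The cost is one degree of freedom in about 300, a slightly less parsimonious model and a line or two of text. No new data are needed.

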 - a. **Open-label period:** ~~At the start of the open-label period, patients must take dexamethasone 10 mg or the equivalent as their corticosteroid premedication. Patients taking more than 10 mg of dexamethasone at the end of the double-blind period should take the higher dose. The corticosteroid dose may then be tapered as described above if the patient is tolerating infusions. However, if a patient's steroid premedication had been decreased in the double-blind period due to their inability to tolerate the premedication regimen as described above, continuation of the reduced dose regimen (as it had been in the double-blind period) may be permitted after consultation with the Medical Monitor.~~

~~Infusions during corticosteroid tapering (and the 2 infusions after the new and stable lower corticosteroid dose is established) should may be performed in the clinic at the study center or at a location other than the study center (eg, at home), as described in detail in the Pharmacy Manual, at the discretion of the Investigator and after consultation with the Medical Monitor.~~

Purpose: *Clarified that oral premedication equivalents are permitted.*

The primary change occurs in Section 5.2.1, Premedication

Revised text:

~~For premedications not available or not tolerated intravenously, equivalents may be administered orally. Oral premedication equivalents are permitted, but must be administered in the presence of a healthcare professional.~~

Purpose: Widened the window for completion of efficacy assessments at study visits.

The primary change occurs in Section 6.2, Efficacy Assessments

Added text:

As noted in Table 1, in situations where a Month 6 (Day 176-183), Month 9 (Day 260-267), and/or Month 12 (Day 365-372) study visit is unable to be completed at the study center due to the COVID-19 pandemic impacting activities at the study center or patient ability or willingness to access the study center, efficacy assessments should be completed as close as possible to the time point per the current Schedule of Assessments, but may be extended as follows: Month 6 up to Day 214; Month 9 up to Day 319; Month 12, up to Day 417, but prior to the first dose of open-label patisiran. Patients may continue to receive double-blind study drug until the Month 12 efficacy assessment is performed.

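### The Month 12 walk-test period closes on the last day of the visit, so a few patients who are still unwell after a late hospitalisation or acute illness have no primary endpoint value

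*Protocol*

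**What the plan says.** Protocol Section 6.2.1 contains three rules that can delay a walk test.

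- After an admission: "Patients who are hospitalized during the study should wait at least 2 weeks after hospitalization before completing a 6-MWT assessment". The same sentence goes on: "less time post-hospitalization may be permitted if, in the opinion of the investigator, the patient is unencumbered due to the recent hospitalization".
- In an acute illness or injury: "the test should not be done and should be rescheduled for another day within the permitted visit window".
- An interrupted or unusable test is to be repeated as soon as possible, within the allowed visit window.

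The same section and Table 1 footnote d set the collection periods. Month 6 runs from Day 2 to Day 214 and Month 9 from Day 215 to Day 319. The last is "Day 320 to Day 372 (for Month 12"). One walk is taken per period: "Within a given time period, the 6-MWT assessment should be performed at whichever visit occurs first".

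The scheduled visits are Day 176-183, Day 260-267 and Day 365-372. Table 2 puts the first open-label dose at Day 379±3. The Amendment 2 summary of changes allows efficacy assessments at "Month 12, up to Day 417, but prior to the first dose of open-label patisiran", but only where the COVID-19 pandemic prevents the visit.

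Under Section 7.2.5.1 the primary endpoint "will be analyzed using a mixed-effects model repeated measures (MMRM) approach", with the contrast at Month 12.

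**The concern.** The delay rules push some walks later, and the calendar leaves no room for that at the one time point that supplies the primary endpoint. The patients affected are not a random subset. The option to shorten the wait lets recovered patients walk and leaves those still weakened without a value, so whether the value is missing depends on current walking ability. Month 6 and Month 9 walks from such a patient stay in the model, but they describe the course before a late admission.

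This is a matter for the protocol. Handling of missing data is left to the SAP (Section 7.2.3), but no analysis can recover a walk that the assessment window did not allow.

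**Working it through.** **Calendar.**

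- Last discharge day that permits a full 14-day wait: 372 − 14 = Day 358.
- Room between the end of the visit and the end of the collection period: Month 6, 214 − 183 = 31 days; Month 9, 319 − 267 = 52 days; Month 12, 372 − 372 = 0 days.
- Earliest and latest first open-label dose: 379 − 3 = Day 376 and 379 + 3 = Day 382. The last day before it is Day 375 to Day 381, so 375 − 372 = 3 to 381 − 372 = 9 days before open-label dosing go unused.

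**The plan's own power figure.** Section 7.1 gives 300 patients, 29 m, SD 75 m and two-sided alpha 0.05, for power above 90%. The weighted effect is 0.7 × 33 + 0.3 × 20 = 29.1 m. With 150 per arm the standard error is 75 × √(2/150) = 8.66 m, and power is Φ(29/8.66 − 1.96) = 91.8%. The stated figure reproduces.

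**How many patients.** The protocol gives no hospitalisation rate for this trial. Section 1.3.1.1 quotes rates per 100 patient-years from the earlier polyneuropathy trial: 71.8 (placebo) and 34.7 (patisiran) for any hospitalisation and/or death, and 18.7 and 10.1 for cardiac hospitalisation and/or death. Carrying them over is an assumption. Patients affected per arm = 150 × rate × days/365, over the 14 days from Day 359 to Day 372:

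| Rate used | Placebo | Patisiran | Total |
|---|---|---|---|
| Any hospitalisation and/or death | 150 × 0.718 × 14/365 = 4.1 | 150 × 0.347 × 14/365 = 2.0 | 6.1 |
| Cardiac hospitalisation and/or death | 150 × 0.187 × 14/365 = 1.1 | 150 × 0.101 × 14/365 = 0.6 | 1.7 |

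That is roughly 2 to 6 of 300. Acute illness and unusable tests would add to it, but the protocol offers no rate for them.

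**Bias.** Suppose the patients without a walk would have covered 40-80 m less than the model predicts for them (an assumption). The bias is then the between-arm difference in the proportion lost, times that deficit.

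- Cardiac rates, 14 days: (0.187 − 0.101) × 14/365 = 0.33%, giving 0.1 to 0.3 m.
- All-cause rates, 14 days: (0.718 − 0.347) × 14/365 = 1.4%, giving 0.6 to 1.1 m.
- All-cause rates over an assumed 21-day blocked span: 0.371 × 21/365 = 2.1%, giving 0.9 to 1.7 m.

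More poor walks would be lost on placebo than on patisiran, so the placebo mean looks too good and the difference shrinks towards zero.

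**Power.** It is 91.6% with 2 Month 12 values lost, 91.2% with 6 and 91.0% with 9. It stays above 90% until about 18 are lost (90.1% at 18, 89.9% at 20).

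**The case against.** A reader might infer that the two-week wait cannot be met and that everyone discharged after Day 358 loses the primary endpoint. The documents do not support that. The wait is a recommendation, and the second half of the same sentence permits a shorter one with no stated minimum. A walk earlier in the period also counts: an early-discontinuation or pre-tafamidis visit from Day 320 on, or a scheduled walk on Day 365 or later before a subsequent admission. A patient without a Month 12 walk still contributes Months 6 and 9 to the model.

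The counts are upper-end. They treat every event as a lost walk, ignore the shorter-wait option, come from a different population and include deaths, whose missing walks the waiting rule does not cause. This stands, and it is why the effect is called small.

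The contrast with Months 6 and 9 can also be challenged, because the illness and repeat-test rules refer to the visit window, which is equally short at all three visits. For those two rules the challenge has force at Months 6 and 9. At Month 12 it makes no difference, since both windows end on Day 372. The post-hospitalisation rule names no visit window, so there the collection period is the limit.

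Finally, the Section 6.2.1 text read here is the Amendment 1 body. The Amendment 2 summary lists Section 6.2.1 and Table 1 among the places changed for the COVID-19 extension, but reports no change to the hospitalisation rule and no relief for an ordinary admission or illness. The current body text should be checked before editing.

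**Conclusion.** The point holds in a narrow form. A patient discharged after Day 358 and still encumbered, or acutely unwell through Day 372, with no earlier walk from Day 320 on and no COVID-19 extension, has no Month 12 value, although open-label dosing has not begun. For the hospitalisation part this is roughly 2 to 6 of 300 patients and probably fewer. The bias is roughly 0.1 to 1.7 m of 29 m, probably towards no effect, and power stays about 91%. These sizes rest on borrowed event rates and on the assumed 40-80 m deficit. The direction rests on patisiran reducing hospitalisation and on the lost patients walking worse than predicted. The size does not threaten the trial's conclusion. The case for acting is that the loss is avoidable at almost no cost.

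**What to change.** In Section 6.2.1 and Table 1 footnote d, allow a Month 12 6-MWT that was delayed by the post-hospitalisation rule, by acute illness or by an unusable test to be done after Day 372 but before the first open-label dose. Extend the Month 12 grouping period to the same limit, so that the walk is assigned to Month 12.

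The cost is two edits to the assessment window, with no change to dosing. There are two limits.

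- Some walks will fall later after the last double-blind dose than the scheduled 7-14 days. With that dose on Day 358, a walk on Day 373 to Day 381 is 15 to 23 days after it.
- Only part of the blocked span is recovered. The discharge cut-off moves from Day 358 to between 375 − 14 = Day 361 and 381 − 14 = Day 367, depending on the open-label dose date.

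How the walks that remain missing are analysed is left to the SAP.
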